7.2 Efficacy assessment

The effectiveness of the intervention on percent time in target glucose range will be assessed using an ANCOVA including treatment and baseline percent time in range. The analysis will be conducted on an intention to treat basis. The result will be presented as the mean difference in the percent time in target range at the end of the study between treatment arms with 95% confidence interval and p value. A statistically significant result ($p < 0.05$) in the direction in favour of the intervention group will be considered to provide evidence of the effectiveness of the intervention.

8 Assessment of Safety

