This marks the end of the 6-week study period. Clinical data (HbA1c) along with total daily insulin requirement and pump settings at the end of the study will be collected. Short questionnaire asking for feedback using the 780G pump with SmartGuard, will be given to parents (optional).

[figure not shown]
Wash-out period: There should be a minimum wash-out period of 3 months for participants willing to enrol for the larger RCT. The 3-month period is chosen to minimise the impact of any carry over of glycaemic impact with AHCL into the larger RCT.

Randomized Controlled Trial (RCT) Phase

This is a **prospective multicentre randomised controlled, two-arm unblinded, parallel study** in free-living conditions, in young children with type 1 diabetes on insulin pump therapy. Participants will be randomised in two groups; either the control group (standard therapy) or the intervention group (AHCL). The control group will be participants on continuous subcutaneous insulin infusion (CSII) with or without CGM (continuous glucose monitoring). The study duration is for 3 months. This phase will be conducted at four tertiary paediatric diabetes centres (Perth Children’s Hospital, WA, Westmead Children’s Hospital, NSW, Women’s and Children’s Hospital, SA, and Royal Children’s Hospital, VIC).

AHCL group: Investigational pump for 3 months OR Control group: Standard CSII for 3 months.

The study design is as shown in the Figure 2 as below.

*Visits 2B,2C, 5C, 5D optional if data requirement from blinded CGM not met, Visit 5 Blinded CGM only for control group.

Figure 2: Study design RCT

VISIT 1

(Eligibility Confirmation, Baseline data collection and commencement of run-in period).

Information sheets will be provided in advance to participants who potentially fit inclusion criteria. HbA1c should be available from last clinic visit within 3 months of Visit 1.

Participants will be checked if they meet the inclusion criteria listed below in Section 5.2. The following data will be recorded:

1. Consent signed by parent and investigator
2. Auxology
 - a. Height
 - b. Weight
 - c. BMI
3. Demographic
 - a. Date of Birth
 - b. Gender
4. Diabetes clinical
 - a. Date of diagnosis
 - b. Current pump/CGM therapy
 - c. HbA1c
 - d. History of severe hypoglycaemia – coma or convulsion or episodes requiring third party assistance (events in last 12 months).
 - e. History of diabetic ketoacidosis (DKA) in the last 12 months

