4.3 Bias

4.4 Blinding and Randomisation

To minimise bias, participants will be allocated to treatment group based on minimisation. Blinding is not possible in this open label study and hence the maintenance of breaking codes is not required.

Minimisation will be used to allocate participants to study group based on the following balancing factors measured at baseline: age at Visit 1 (<6 years, 6 years and above), time in target range (<55%, greater or equal to 55%) collected from blinded sensor data, and study site. Minimisation is a method of ensuring excellent balance between groups for known prognostic factors(20). The Minimpy program (MinimPy)(19) will be used to allocate participants. Allocation will be undertaken by the delegated persons at Perth Children's Hospital.

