9.1 Statistics and Interim Analysis

Feasibility Phase

No statistical tests will be conducted with the difficulties encountered/solutions identified at the weekly meetings of the study team. Rather, all difficulties encountered will be discussed on a weekly basis and be collated into a single table at the end of the feasibility phase. This information will be used to design the manual of operations for the larger RCT.

Recruitment rate will be presented as a rate of recruitment per week and retention rate will be presented as a proportion of recruited participants that continued to wear the device to the end of the feasibility phase.

The mean, standard deviation, median, and interquartile range will be presented for insulin to carbohydrate ratio, insulin active time, and percent time in various glycaemic ranges at the end of the phase.

No interim analyses are planned apart from the DSMB safety review reported above.

RCT Phase

Data collected at baseline and Visit 6 will be used to assess the effectiveness of AHCL therapy as compared to standard therapy.

To test for an effect of treatment group on the primary outcome, an ANCOVA including treatment, baseline percent time in range adjusting for minimisation factors will be conducted on an intention to treat basis. Multiple imputations will be used to handle missing data: a multivariate normal imputation approach will be taken. Results will be presented as the mean difference in the percent time in target range at the end of the study between treatment arms with 95% confidence interval and p value.

Model residuals will be used to assess model fit. If the residuals indicate poor model fit, the outcome variable will be transformed and the model refitted and evaluated. If poor model fit cannot be addressed, nonparametric analysis will be performed.

In the event that residuals are not normally distributed: the Mann–Whitney–Wilcoxon (Wilcoxon Rank-Sum) Test will be employed if raw data are symmetric; if raw data are non-symmetric, bootstrap methods will be used to test the difference between groups.

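### Sections 7.2 and 9.1 list different covariates for the same primary ANCOVA; the list beside the success rule omits age group and study site, both used in minimisation

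*Protocol*

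**What the plan says.** Protocol section 7.2 states that effectiveness on percent time in range will be "assessed using an ANCOVA including treatment and baseline percent time in range", by intention to treat. It then sets the decision rule: a significant result "in the direction in favour of the intervention group will be considered to provide evidence of the effectiveness of the intervention". No other section states a success rule.

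Protocol section 9.1, RCT Phase, covers the same test. It opens "To test for an effect of treatment group on the primary outcome" and specifies "an ANCOVA including treatment, baseline percent time in range adjusting for minimisation factors will be conducted on an intention to treat basis". The reported quantity is the same as in 7.2: the mean difference at study end with its 95% confidence interval and p value.

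Section 4.4 supplies the factors: "Minimisation will be used to allocate participants to study group based on the following balancing factors measured at baseline". They are age group (under 6 years; 6 and above) and "time in target range (<55%, greater or equal to 55%) collected from blinded sensor data, and study site". Section 4.2 gives the number of sites: "This phase will be conducted at four tertiary paediatric diabetes centres".

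No section says which covariate list takes precedence, and neither analysis is labelled a sensitivity analysis.

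**The concern.** A primary analysis should be written so that two statisticians fit the same model. Here the outcome, method, analysis set and reported estimate agree, but the covariates do not, and the decision rule stands beside the shorter list.

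Two things follow. First, the verdict in a borderline trial could depend on which section is followed. The trial is open label, section 9.1 rests its lack of multiplicity correction on a clearly specified primary outcome, and section 9.4 requires deviations from the original plan to be reported. All three call for a single model.

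Second, the shorter model does not match the allocation. Minimisation removes chance imbalance in age group and site, so the treatment estimate varies less than a model without those terms assumes. If the factors are prognostic beyond baseline TIR, that model reports too large a standard error. The same ANCOVA also serves the continuous secondary outcomes, so the ambiguity carries over to them.

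**Working it through.** **The plan's own figure.** Section 9.2 gives 31 per group for 80% power to detect 8 points with SD 11.5, two-sided 0.05. The normal formula gives 2 × (1.960 + 0.842)² × 11.5² / 8² = 32.4, so 33 per group; 31 per group gives 78.2% power. Allowing for 10% dropout, 62 / 0.9 = 68.9, so 69 against the 70 planned. These agree closely enough. Section 9.2 uses no covariates, so the choice of model does not alter the planned number.

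**Covariates side by side.**

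| Term | 7.2 | 9.1 |
|---|---|---|
| Treatment | yes | yes |
| Baseline TIR | yes | yes |
| TIR category (1 df) | not named | yes |
| Age group (1 df) | not named | yes |
| Study site (3 df) | not named | yes |

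With 62 children the residual degrees of freedom are 62 − 3 = 59 under 7.2 and 62 − 8 = 54 under 9.1.

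**Expected standard errors.** The protocol gives the SD. The correlation between baseline and final TIR is not given; take 0.5.
- Residual SD after baseline: 11.5 × √(1 − 0.5²) = 9.96.
- SE under 7.2: 9.96 × √(4/62) = 2.53.
- If site and age explain a share R of the residual variance, the adjusted SE is about 2.53 × √(1 − R), or 2.26 at R = 20% and 2.12 at R = 30%. Simulation gives about 2.28 and 2.13, slightly higher because of the extra terms. At R = 0 it is 2.55 to 2.57.

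**Why 7.2 becomes conservative.** With perfect balance on the factors, the 7.2 estimate has the smaller true SE but is tested against 2.53. The effective critical value is 2.00 × 2.53 / 2.26 = 2.24 at R = 20% (two-sided error about 2.5%) and 2.00 × 2.53 / 2.12 = 2.39 at R = 30% (about 1.7%). Minimisation with a random element balances less than perfectly, so simulated error at R = 20% is 3.3%, against 4.8 to 5.1% with adjustment. Power at 8 points there is 88 to 90% against about 92%.

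**Both models fitted to the same simulated trials.** There were 3,000 minimised trials per row (Monte Carlo error about 0.4 points at 5%). Assumptions: minimisation probability 0.8, sites sharing 40/20/20/20% of children, 35% aged 6 or above, and site SD and age effect both set to 0, 4 or 6 points. The 9.1 model includes the TIR category.

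| True effect | Site SD / age effect | p < 0.05, 7.2 | p < 0.05, 9.1 | Either | Disagree | SE, 7.2 | SE, 9.1 |
|---|---|---|---|---|---|---|---|
| 0 | 0 / 0 | 5.0% | 4.9% | 5.7% | 1.4% | 2.53 | 2.56 |
| 0 | 4 / 4 | 2.9% | 4.1% | 4.5% | 1.9% | 2.52 | 2.36 |
| 0 | 6 / 6 | 2.6% | 5.4% | 5.6% | 3.2% | 2.53 | 2.08 |
| 8 | 0 / 0 | 86.6% | 85.6% | 87.5% | 2.8% | 2.53 | 2.56 |
| 8 | 4 / 4 | 88.4% | 91.0% | 91.8% | 4.3% | 2.53 | 2.37 |
| 8 | 6 / 6 | 89.8% | 95.9% | 96.2% | 6.7% | 2.53 | 2.09 |

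The strongest setting lies a little beyond R = 30%. Site variance is 36 × (1 − 0.28) = 25.9 and age variance 36 × 0.35 × 0.65 = 8.2, against a remaining variance of 0.75 × (132.25 − 36 − 8.2) = 66.0, so R is about 34.1 / 100.1 = 34%. This is why its disagreement at 8 points exceeds the 2 to 5% found over R = 0 to 30%. With a true effect of 5 points, which is not the design effect, disagreement ran from 5.3% to 18.8%.

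**The case against.** The strongest reply is that 7.2 is a summary and 9.1 the full specification. The wording in 7.2 says the model includes two terms, which does not close the list, and 9.1 is the statistics section, where imputation and residual checks are also set out. On that reading there is one analysis. This is plausible and keeps the point modest. It does not settle the matter, because 7.2 names model terms, carries the decision rule and does not refer to 9.1. Covariate coding can be left to an analysis plan, but a plan following either section could still be said to depart from the other.

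Three stronger inferences are tempting, and the protocol does not support them.
- **That 7.2 ignores the minimisation factors altogether.** It contains continuous baseline TIR, which largely carries the TIR category. Only age group and site are missing.
- **That the 7.2 interval is too wide whenever site or age predicts TIR.** What counts is prediction of end-of-study TIR beyond baseline TIR. If there is none, the two SEs are almost equal (2.53 and 2.56).
- **That there are two primary p values and a material risk of a false positive from picking the better.** There are two candidate models, and taking the smaller p value rejects in only 4.5 to 5.7% of null trials. The shorter model errs on the safe side.

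It is also fair that every magnitude rests on values the protocol does not give, and that simulated power under either model exceeds the planned 80%.

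**Conclusion.** The inconsistency is real and should be corrected: one primary outcome has two covariate lists with no stated precedence, and the success rule stands beside the list that omits two of the three minimisation factors.

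Its practical effect is modest. If site and age carry no information beyond baseline TIR, the models are nearly interchangeable. If they explain up to 30% of the residual variance, following 7.2 literally gives an SE of 2.53 where about 2.13 is attainable and a test run at about 1.5 to 3% instead of 5%, with some loss of power. The two models reach different conclusions in roughly 1 to 3% of null trials and 2 to 5% of trials at the design effect, slightly more with stronger factors. The harm is lost precision and room for discretion in a borderline result; it is not an inflated type I error.

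These sizes assume 62 analysed children, a baseline correlation of 0.5 and a minimisation probability of 0.8. The contradiction itself rests on no assumption.

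**What to change.** Write one identical primary model in both 7.2 and 9.1: treatment, continuous baseline TIR, age group (under 6; 6 and above) and study site. State in both places that continuous baseline TIR stands in for the TIR category used in minimisation. Pointing 7.2 at the present 9.1 text would not be enough, because the minimisation factors named there include the TIR category and the lists would still differ. State in 7.2 that the success rule applies to this model only.

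The cost is a sentence in each section and 4 degrees of freedom (age group 1, site 3), leaving 62 − 7 = 55. If the factors turn out not to be prognostic, the SE rises only from 2.53 to about 2.55. The sample size does not change.

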8.1 Risks and benefits

1. There is a small risk of insulin pump site and glucose insertion site bruising, or skin reaction and/or haematoma. However all participants have used insulin pumps and most would have used sensors previously. This risk is expected to be similar to the current insulin pump and sensor issues in the clinic population.
2. Inaccuracy of sensor glucose with paracetamol. Taking medications that contain paracetamol may falsely raise sensor glucose readings. This may result in an over-delivery of insulin. If using paracetamol, all participants are advised to use glucometer to do blood glucose checks to make treatment decisions. This information is provided to all families at the time of commencement of sensor in clinic. Participants on HCL will also be advised to turn off the Auto correction feature, and consider turning off SmartGuard feature.
3. Risk of hypoglycaemia/hyperglycaemia: Any patient receiving insulin at any time has the potential to develop hyper or hypoglycaemia. These devices specifically aim to minimise the potential for that risk. The sensor glucose levels of all study participants are available to parents/caregivers in real time which will enable them to take appropriate clinical action as required.

As the AHCL system is semi-automated and is dependent on the sensor glucose levels and the algorithm for delivery of background basal insulin, it could potentially have a risk of over-delivery or under-delivery of insulin.

- a) An over-delivery of insulin can cause **hypoglycaemia**. Although this is more likely to be mild, the risk, albeit small, is that of glucose level falling < 3mmol/l and if prolonged, can cause severe hypoglycaemia (coma or convulsions or altered consciousness requiring third party assistance for treatment).
- b) An under-delivery of insulin can cause **hyperglycaemia**. Glucose levels if persistently high can cause ketosis and if not corrected, can lead to diabetes ketoacidosis. This will require intravenous fluid hydration and repeated insulin doses for correction.

The management of the risks above are outlined in section 8.2 of the protocol as below.

- For severe hypoglycaemia, intramuscular glucagon can be administered.
- For ketosis > 0.6mmol/l with blood glucose > 15mmol/l, insulin (rapid-acting) is administered with an insulin pen.
- Contact with research team – as may require hospitalisation

This is taught to every family at the time of diagnosis of T1D and review of their knowledge is established in subsequent clinic follow-ups.

Furthermore, the system enables remote monitoring. The parent/caregiver will have real-time glucose readings of the young child on the phone allowing continuous glucose monitoring. High and low alerts will be enabled on the phone which will permit immediate correction of hypoglycaemia/hyperglycaemia.

8.2 Safety

This is a cohort of young children with T1D supervised by their parents/caregivers.

Participants will be contacted on a weekly basis (or more frequently as required) during the entire duration of the feasibility phase and for at least 4 weeks of the larger RCT after commencement of AHCL to review progress. During the feasibility phase, the research nurse will also follow the participant in real-time. Real-time glucose levels will also be available to the caregiver/parent at all times.

- a. Participants with high blood/sensor glucose levels will be advised to test for blood ketones.
- b. Participants with hypoglycaemia will be advised to take appropriate clinical action.
- c. Weekly review of time spent in hypoglycaemia range will be evaluated by the research doctor. Any instance of a week where percentage of time spent <3.9 mmol/l exceeds 8% and/or percentage of time <3 mmol/L exceeds 2 % will be recorded as an adverse event.
- d. Participants using the AHCL system will be informed to contact the research diabetes educator if they experience technical issues with the sensor and/or system and to revert to manual mode (standard pump) in the interim.
- e. Participants in the control group will be advised to follow the clinical pathway while participants in the intervention group will be advised to contact the research doctor/diabetes educator.
- f. In the event of device (pump) failure, the participant will be advised to switch to their standard pump therapy (own pump) and contact the research doctor/diabetes educator.
- g. Patients are educated regarding awareness of insulin infusion failure (rising blood glucose levels and ketones) and how to manage this (using standard injected subcutaneous insulin, and change insulin infusion set).
- h. Any admissions to hospital for DKA or severe hypoglycaemia will be reported to the principal investigator within 24hrs with notification to the lead site.
- i. Establishment of Data and Safety Monitoring Board (DSMB) to review progress

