 - a. HbA1c
 - b. Total daily dose of insulin (mean of previous 7 days)
 - c. Severe hypoglycaemia in the run-in period
 - d. Diabetic ketoacidosis in the run-in period
 - e. Hospital admissions in the run-in period
2. Review carbohydrate (CHO) counting and offer dietetic support if needed
3. Pump upload and review of settings
4. Review of hypoglycaemia/hyperglycaemia management.

The control group will continue on their insulin pump therapy with or without CGM. They will attend the 3-monthly regular clinic appointments.

The intervention group will use the study device with the compatible CGM. They will attend additional visits required for device training and to review the pump settings. They will continue to attend their 3-monthly clinic appointments.

If needed, Visit 3 and 4A can be combined for intervention group.

VISIT 4 (Only for participants randomised to AHCL arm)

The additional visits for the HCL group are for device training to support the use of HCL.

Visit 4A: Pump training (2 hours)

Parents will be trained on how to use the Medtronic 780G insulin pump. They will be provided with a compatible meter (which communicates with the pump) along with the glucose strips for the study.

Visit 4B: CGM training (2 hours)

They will be instructed on how to link CGM on the Medtronic 780G pump and issued with compatible next generation sensor and transmitter, as well as CGM user guide. Initial low and high alarms will be set at 4.0mmol/L and 15mmol/L respectively, although these can be changed according to individual preference. Sensor naïve individuals will have familiarisation phase of 7 to 10 days to get used to wearing a sensor.

Visit 4A and 4B could be combined for participants familiar with sensors.

Visit 4C: Commencement of AHCL (1-2 hours)

Once CGM data has been established for a minimum of 3 to 7 days, participant returns for face-to-face instruction on AHCL use and initiation of 'SmartGuard'. During this visit, the sensor will be replaced to demonstrate sensor warm up and AHCL initiation, and provide an opportunity for those unfamiliar with CGM use to practice a sensor change with supervision.

Participants will subsequently have weekly communication via phone call or email for support for the following 4 weeks, and upload their pump weekly. Investigators will log all time spent training and in communication with participant. Communication can be more often – as per clinical need, and logged.

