Visit 4D: Review of AHCL (after 4 weeks from commencement of AHCL, 1 hour)

Face-to-face meeting to upload insulin pump, review CareLink reports and revise settings (CHO ratio and Insulin action time)

Participants will be issued with enough consumables for the study.

Research staff will review CGM data at 8 weeks' with participants encouraged to contact the team if support/assistance required.

VISIT 5 (11 weeks after randomisation for control arm only)

Visit 5A: Insertion of blinded CGM: This constitutes first of the two sensors, each sensor provides data for 7 days. Parents will be instructed to test their children for a minimum 3 to 4x/day using the study meter.

Visit 5B: Insertion of 2nd blinded CGM: Participants will return 7 days after sensor insertion to remove and download the first week of CGM data. The study meter will be uploaded. A new sensor will be inserted and a fresh transmitter attached.

A total of 2 weeks of blinded sensor is required with at least 10 days of data. In participants who do not meet this requirement, repeat sensors will be offered till a maximum of 4 attempts of data collection

Visit 5C: Insertion of 3rd blinded sensor (if applicable)

Visit 5D Insertion of 4th blinded sensor (if applicable)

VISIT 6 (1 week after last blinded sensor) **End of RCT Phase**

The following data will be collected:

1. Auxological
 - a. Height
 - b. Weight
 - c. BMI
2. Diabetes clinical
 - a. HbA1c
 - b. Total daily dose of insulin (mean of previous 7 days)
 - c. Pump upload (for intervention group)
 - d. Severe hypoglycaemia since Visit 5 for Control arm / Visit 4d for Intervention arm
 - e. Diabetic ketoacidosis since Visit 5 for Control arm / Visit 4d for Intervention arm
 - f. Hospital admissions since Visit 5 for Control arm / Visit 4d for Intervention arm
3. Psychology measures: Psychological scales will be administered to parents on an electronic platform.
 - a. Functional health status: Quality of life (QOL) WHO 5, EQ5D
 - b. Fear of hypoglycaemia: Hypoglycaemia fear survey Parent
 - c. Diabetes-related distress: Problem Areas in Diabetes PAID-Parent version
 - d. Anxiety: GAD-7
 - e. Sleep quality: Pittsburgh Sleep Quality Index
 - f. Technology acceptance and satisfaction: DTQ
4. 24-hour food recall interview (to capture dietary pattern)
5. Parents of participants will be offered a semi-structured interview at the end of the study to share the lived experiences with use of new technology.

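### Section 8.2(c) makes a week above the CGM hypoglycaemia thresholds an adverse event, but weekly CGM review in the RCT is scheduled only for AHCL children, so raw counts of this event are not comparable between arms

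*Protocol*

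**What the plan says.** **The rule.** Section 8.2(c) opens: "Weekly review of time spent in hypoglycaemia range will be evaluated by the research doctor". A week in which time below 3.9 mmol/L is above 8%, and/or "percentage of time <3 mmol/L exceeds 2 % will be recorded as an adverse event". Neither an arm nor a set of weeks is named.

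**AHCL arm.** Section 8.2 sets weekly contact "for at least 4 weeks of the larger RCT after commencement of AHCL to review progress". In Section 4.2, under Visit 4 (AHCL arm only), Visit 4C gives these families "weekly communication via phone call or email for support for the following 4 weeks, and upload their pump weekly". Later in the same visit block: "Research staff will review CGM data at 8 weeks". The Visit 6 pump upload is also for the intervention group only.

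**Control arm.** Section 4.2 states: "The control group will be participants on continuous subcutaneous insulin infusion (CSII) with or without CGM". After randomisation these children attend 3-monthly clinics. At Visit 5, from week 11, they wear two blinded 7-day study sensors, with repeats up to four if data are insufficient. The first week is downloaded at 7 days. No upload of a control child's own CGM after randomisation is specified, and nothing says that the blinded data are screened under 8.2(c).

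**The concern.** The rule is worded for everyone, but the routine for detecting the event is built around AHCL use. A poor week 3 on AHCL is uploaded, reviewed and recorded as an adverse event. The same week in a control child is not looked for, whether or not the child has a personal sensor.

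A raw count, or a percentage of children with at least one such event, would then partly measure how many weeks were inspected. Section 8.3 has the DSMB review accruing data and advise on conduct, and adverse events from a two-arm trial are normally read by arm. An excess on AHCL produced by closer inspection could be taken for a hypoglycaemia signal, or could hide a real benefit.

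**Working it through.** The protocol gives no rate or count for this event, so there is no figure to reproduce. The check asks what raw counts would look like if true hypoglycaemia were identical in the two arms.

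**Inputs**
- Children per arm: 70 planned in two equal groups (Section 9.2), so 35.
- Screened AHCL weeks, k_A: 4 (the weekly-contact period, without the extra 8-week review) up to 12 (3 months taken as 12 weeks). Twelve is an upper bound, because AHCL starts only after training and 3 to 7 days of CGM.
- Screened control weeks, k_C: 2 (planned blinded sensors), 4 (maximum), or 0 (blinded data not screened).
- Weekly probability p of crossing a threshold: not in the protocol. Assumed equal in both arms, 5% for illustration, range 2% to 20%.

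**Formulas**
- Expected events per arm = 35 × p × k
- Ratio of raw counts = k_A / k_C, which depends on neither p nor the sample size
- Share of children with at least one event = 1 − (1 − p)^k, taking weeks as independent

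**Results at p = 5%**

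| Screened weeks, AHCL v control | Ratio | Expected events | Children with at least one |
|---|---|---|---|
| 4 v 4 | 1 | 7.0 v 7.0 | 18.5% v 18.5% |
| 4 v 2 | 2 | 7.0 v 3.5 | 18.5% v 9.8% |
| 12 v 4 | 3 | 21.0 v 7.0 | 46.0% v 18.5% |
| 12 v 2 | 6 | 21.0 v 3.5 | 46.0% v 9.8% |
| 4 v 0 | undefined | 7.0 v 0 | 18.5% v 0% |
| 12 v 0 | undefined | 21.0 v 0 | 46.0% v 0% |

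For example, 35 × 0.05 × 4 = 7.0 and 35 × 0.05 × 2 = 3.5.

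**Range of p.** From 2% to 20%, the 4 v 2 case runs from 2.8 v 1.4 to 28.0 v 14.0 events. The 12 v 2 case runs from 8.4 v 1.4 to 84.0 v 14.0. The ratios stay at 2 and 6.

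**If AHCL truly halves the weekly rate.** The apparent ratio is 0.5 × k_A / k_C. That is 0.5 × 4/2 = 1.0, so the benefit disappears, or 0.5 × 12/2 = 3.0, so it looks like a threefold excess.

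**With equal windows.** Two screened weeks in each arm give 35 × 0.05 × 2 = 3.5 v 3.5, ratio 1.

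**The case against.** The strongest reply is that this is device surveillance and not a comparison. Section 8.2 opens with contact timed from the start of AHCL, and watching an investigational device more closely in young children is deliberate. Section 9.1 names no between-arm test of adverse events. The safety question is answered elsewhere: the primary safety outcome in Section 4.9 is clinical severe hypoglycaemia, and Section 4.1 lists % CGM time <3.9 and <3.0 mmol/L as endpoints. All of that stands. It limits the consequence but does not settle the scope of 8.2(c), which makes these weeks adverse events without restricting the arm.

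A second reply is that Section 9.1 uses sensor hours as exposure for CGM-derived counts. If applied here, that would remove much of the imbalance wherever control CGM is reviewed. But it is written for secondary count outcomes, and this event is not among the endpoints in Section 4.1. It cannot help where control CGM is not reviewed, does not correct the percentage of children with an event, and would set AHCL start-up weeks against control weeks from 11 onward.

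A reader might also infer three stronger things that the protocol does not support:
- **Only AHCL children have CGM, so the control count must be zero.** Controls have 2 to 4 weeks of study CGM after randomisation, and Section 6.3 says most of the cohort already uses sensors. Zero follows only if control data are never screened, which is not stated.
- **AHCL weeks are reviewed weekly for 13 weeks (35 × 13 = 455 child-weeks).** The schedule has weekly contact for at least 4 weeks and one CGM review at 8 weeks.
- **The trial's hypoglycaemia comparison is biased.** The endpoints named above do not depend on 8.2(c).

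**Conclusion.** The point holds for this one event type. The protocol fixes both the adverse event definition and the unequal means of detecting it, and leaves open whether control CGM is screened. Following the schedule as written, raw counts would show an AHCL:control ratio of about 2 under identical glycaemia. The ratio is 1 only in the case most favourable to the plan: AHCL review stops at 4 weeks, and controls use, and have screened, all four sensors. It reaches 6 if all 12 AHCL weeks are screened against two control weeks, and every event falls in AHCL if control data are not screened.

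The ratios assume only an equal weekly rate in the two arms. The event counts rest also on the assumed p and on 35 children per arm. The matter is one of scope and reporting and should be settled before adverse events are tabulated by arm. It does not touch the primary safety outcome or the time-below-range endpoints.

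**What to change.** - State in Section 8.2(c) which arms and which CGM weeks the rule covers, including whether the controls' blinded sensor weeks are screened. Leave the weekly review and the thresholds as they are.
- Report threshold-week events in full, on a separate line labelled as not comparable between arms, and do not pool them into by-arm adverse event totals. They then stay visible to the DSMB and in the final report.
- Make any between-arm comparison only over the end-of-study CGM window measured in both arms, per CGM-week.
- First reconcile the timing of that window. Section 4.2 (Visit 5) starts blinded CGM at week 11 for controls only, while Section 7.1 describes a 2-week blinded recording starting 13 to 15 weeks after randomisation.
- Reconcile Section 8.1, which says that all participants' sensor glucose is available to parents in real time, with controls who may have no CGM and whose study sensors are blinded.

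The cost is wording and one extra table, using CGM data that the primary outcome already requires.
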